6.5. Dose Modification

Dose modifications of JNJ-3989 and NA (increase or decrease of dose level) are not permitted. For PegIFN- α 2a, dose adjustment guidelines are recommended for participants who develop

^a Not applicable for participants in countries that do not allow PegIFN- α 2a self-injection, where weekly administration of PegIFN- α 2a must be performed at the study site by the investigator or his/her designee.

laboratory abnormalities during PegIFN- α 2a treatment, as recommended in the locally approved prescribing information for PegIFN- α 2a. The Pegasys USPI has been provided as an example in [Table 2](#) below.

Table 2: PegIFN- α 2a Hematological Dose Modification Guidelines

Laboratory Values	Recommended Dose
ANC <750 cells/mm ³	Reduce to 135 μ g
ANC <500 cells/mm ³	Discontinue treatment until ANC values return to more than 1,000 cells/mm ³ . Reinstitute at 90 μ g and monitor ANC.
Platelet <50,000 cells/mm ³	Reduce to 90 μ g
Platelet <25,000 cells/mm ³	Discontinue treatment

ANC: absolute neutrophil count

Source: [Pegasys USPI](#)

For participants who prematurely discontinue PegIFN- α 2a, treatment with PegIFN- α 2a may be restarted according to the recommendations from the locally approved prescribing information for PegIFN- α 2a.

6.5.1. NA Treatment Completion

All participants will receive the last dose of JNJ-3989 at Week 24 and the last dose of PegIFN- α 2a at Week 23 (Arms 1 and 2) or Week 11 (Arm 3). They will start the FU Period after the Week 24 visit. If all of the following NA treatment completion criteria are met based on the Week 24 results, treatment with NA will be stopped at the next scheduled visit (ie, FU Week 2):

- The participant has ALT <3x ULN, AND
- The participant has HBV DNA <60 IU/mL at Week 24 and HBV DNA <LLOQ at the previous visit, or HBV DNA <LLOQ at Week 24, AND
- The participant is HBeAg-negative, AND
- The participant has HBsAg <100 IU/mL.

Note: Participants who are close to meeting the protocol-defined NA treatment completion criteria with the Week 24 results, and do meet the criteria based on the FU Week 2 results may be allowed to stop NA at FU Week 4, after consultation with the Sponsor. In case of ALT elevation \geq 3x ULN at Week 24, the investigator must consider different potential causes of increased ALT to ensure appropriate work up and management as needed. If the ALT elevation is unrelated to HBV activity and/or <3x ULN by FU Week 2, NA completion may be considered at the discretion of the investigator and in consultation with the sponsor.

Participants who do not meet the above criteria based on the Week 24 or FU Week 2 results should continue NA treatment during the 48-week FU Period.

Participants who meet the above-mentioned NA treatment completion criteria will be monitored closely during the 48-week FU Period with a study visit at least once every 4 weeks. NA treatment should be re-started in accordance with the NA re-treatment criteria (see Section [6.5.2](#), NA Re-treatment Criteria During Follow-up, for more details).

The investigator should consider to re-start NA treatment per local standard of care at the EOS visit (Follow-up Week 48) for participants who met the NA treatment completion criteria based on the Week 24 (or FU Week 2) results, who did not re-start NA treatment during the follow-up phase, and who did not achieve and maintain HBsAg seroclearance. NA will not be provided by the sponsor after the final study visit.

If a participant prematurely discontinues JNJ-3989 (ie, before Week 24), follow-up assessments should be obtained as per the [Schedule of Activities](#) until 48 weeks after the end of JNJ-3989 treatment, unless the participant withdraws consent. NA treatment may be continued or, in consultation with the sponsor, discontinued, based on the above-mentioned NA treatment completion criteria.

If a participant prematurely discontinues PegIFN- α 2a (ie, before Week 23 [Arms 1 and 2] or before Week 11 [Arm 3]), treatment with JNJ-3989 and NA should be continued as planned.

6.5.2. NA Re-treatment Criteria During Follow-up

Participants who meet the protocol-defined NA treatment completion criteria based on the Week 24 (or FU Week 2) results should complete NA treatment at FU Week 2 (or FU Week 4) as outlined in Section 6.5.1, NA Treatment Completion, and will be monitored closely during the follow-up period with a study visit at least once every 4 weeks. They should re-start NA treatment immediately in the event of:

- Signs of decreasing liver function based on laboratory findings (eg, International Normalized Ratio [INR], direct bilirubin) or clinical assessment (eg, ascites, hepatic encephalopathy).
- HBV DNA value of $>1,000,000$ IU/mL (irrespective of confirmation and/or ALT increase).

Note: A post-treatment HBV DNA value of $>100,000$ IU/mL should trigger re-testing of ALT/AST, HBV DNA, and total and direct bilirubin within a maximum of 7 days from receipt of the data and further repeats as necessary (ie, weekly until HBV DNA returns to $<100,000$ IU/mL). A post-treatment HBV DNA value of $>20,000$ IU/mL (but $<100,000$ IU/mL) should trigger a re-test within 14 days. At all times, additional re-testing of the above parameters should be performed at the investigator's discretion.

In addition, re-start of NA treatment should be considered in the following cases:

- Confirmed post-treatment HBeAg seroreversion (HBeAg positive after it was negative at NA completion), OR
- Confirmed (at least 4 weeks apart) post-treatment increases in HBV DNA $>2,000$ IU/mL and ALT $>5x$ ULN, OR

Note: A post-treatment ALT value of $>5x$ ULN should trigger re-testing of ALT, AST, ALP, total and direct bilirubin, INR, albumin, and HBV DNA on a weekly basis until ALT and AST levels have returned to $<5x$ ULN. At all times, additional re-testing of these parameters should be performed at the investigator's discretion.

- Confirmed (at least 4 weeks apart) post-treatment increases in HBV DNA $>20,000$ IU/mL.

The decision to re-start NA treatment should take into consideration the dynamics of HBsAg, HBV DNA and/or ALT values and should be discussed with the Sponsor.

To avoid delays in decision making, sites are encouraged to run local re-testing in parallel with central re-testing in the situations described above that require more frequent re-testing. Local test results are to be recorded in the CRF and/or source documents, including information on the HBV DNA assay used. In addition, to avoid delays in NA re-treatment, it should be considered to dispense NA to participants who potentially met the NA re-treatment criteria (eg, pending confirmation) and who will not be available to come to the study site immediately at the time the confirmatory test results will become available. This should ensure that the participant can immediately re-start NA treatment if indicated, upon direct confirmation by the investigator.

In case NA treatment is re-started, participants will be followed until the end of the study or until clinical stabilization, whichever comes later.

NA re-treatment criteria during follow-up are presented graphically in Section 10.12, Appendix 12.

Management of intervention-emergent ALT/AST elevations is discussed in Section 8.3.6.2, Intervention-emergent ALT/AST Elevations.

6.6. Continued Access to Study Intervention After the End of the Study

Refer to Section 6.7 of the Master Protocol PLATFORMPAHPB2001.

The investigator should consider to re-start NA treatment per local standard of care at the EOS visit (Follow-up Week 48) for participants who met the NA treatment completion criteria based on the Week 24 (of FU Week 2) results, who did not re-start NA treatment during the follow-up phase, and who did not achieve and maintain HBsAg seroclearance. NA will not be provided by the sponsor after the final study visit.

6.7. Treatment of Overdose

For this study, any dose of JNJ-3989 exceeding the protocol-specified dose with $\geq 25\%$ and any dose of NA (ETV, tenofovir disoproxil, or TAF) greater than the prescribed dose (refer to Section 6.1, Study Intervention(s) Administered), will be considered an overdose. Any dose of PegIFN- $\alpha 2a$ greater than the prescribed dose will be considered an overdose. The Sponsor does not recommend specific treatment for an overdose.

In the event of an overdose, the investigator or treating physician should:

- Contact the Medical Monitor immediately.
- Evaluate the participant to determine, in consultation with the Medical Monitor, whether study intervention should be interrupted or whether the dose should be reduced.
- Closely monitor the participant for AE/SAE and laboratory abnormalities.

- Obtain a plasma sample for PK analysis as soon as possible from the date of the last dose of study intervention if requested by the Medical Monitor (determined on a case-by-case basis).
- Document the quantity of the excess dose as well as the duration of the overdosing in the CRF.

6.8. Concomitant Therapy

An overview of ISA-specific disallowed medication is provided in [Table 3](#).

Local guidelines on the use of live vaccines in participants receiving PegIFN- α 2a should be followed, including for the second dose of Sputnik V (which contains rAd5, with a theoretical risk of replication competence). Sputnik Light, which is the first dose of Sputnik V (with rAd26) is not considered a live vaccine. See below for further guidance on the use of COVID-19 vaccines.

Note that locally approved COVID-19 vaccines (including those that received emergency use authorization or conditional marketing authorization) are allowed throughout the study. For participants receiving PegIFN- α 2a the following recommendations should be applied to accommodate COVID-19 vaccination during the Treatment Period:

- COVID-19 vaccine and PegIFN- α 2a should not be administered on the same day.
- If required, PegIFN- α 2a injection can be delayed up to 2 days. The next PegIFN- α 2a injection should be administered at the scheduled time.
- If required, skipping a PegIFN- α 2a injection may be considered after consultation with the Sponsor.
- Vaccination with Sputnik V should take above-mentioned consideration about live vaccines into account.

All COVID-19 vaccination-related data (eg, COVID-19 vaccination, AEs, AE management) should be appropriately captured in the CRF and source documents. Refer to the COVID-19 vaccine and/or PegIFN- α 2a prescribing information for more details.

For general concomitant therapy considerations, refer to Section 6.5 of the Master Protocol PLATFORMPAHPB2001.

Table 3: Disallowed Medication**Disallowed from 3 years prior to screening until end of follow-up:**

- IFN, other than the PegIFN- α 2a taken in the context of this study.

Disallowed from 1 year prior to baseline until end of follow-up:

- Any oligonucleotide-based treatment (eg, siRNA, nucleic acid polymers, antisense oligonucleotides), other than the study intervention taken in the context of this study.

Disallowed from 6 months prior to screening until end of follow-up:

- Any investigational agent, investigational vaccine, invasive investigational medical device, or investigational biological product (other than the study intervention taken in the context of this study).
Note: For investigational COVID-19 vaccines administered within 6 months prior to screening, an exception will be made as long as the vaccine has been approved (or received emergency use authorization or conditional marketing authorization) at the time of screening.

Disallowed from 6 months prior to baseline until end of follow-up:

- Any systemically (eg, intravenously, intramuscularly, orally, subcutaneously) administered medication that directly or indirectly interferes with immune responses (eg, cyclosporine, interleukins, systemic corticosteroids exceeding 5 mg of prednisolone equivalent/day).

Disallowed from screening until end of follow-up:

- Any anti-HBV drug (including vaccines) other than the study intervention taken in the context of this study.
Notes:
 - NA standard of care treatment is allowed between screening and baseline.
 - Prior hepatic treatment with herbal or nutritional products is allowed but should be stopped at screening.

Disallowed from screening until end of study intervention:

- Products containing *Hypericum perforatum* (St. John's wort).
- Biotin (>1 mg daily dose), either taken alone or as part of a multivitamin formulation.
Note: The use of other vitamins is allowed.
- Topical steroids (>7 days) under occlusive dressing.

The prescribing information for ETV, tenofovir disoproxil, TAF, and PegIFN- α 2a should be consulted for any additional prohibited medication. In case of flu-like symptoms after administration of PegIFN- α 2a, acetaminophen/paracetamol up to a maximum of 2 g per 24 hours and a maximum of 6 g per week is allowed.

Medications requiring subcutaneous injection (other than JNJ-3989 and PegIFN- α 2a; eg, insulin) should be administered in a different location than the JNJ-3989 and PegIFN- α 2a injection sites.

7. DISCONTINUATION OF STUDY INTERVENTION AND PARTICIPANT DISCONTINUATION/WITHDRAWAL

If a participant prematurely discontinues JNJ-3989 (ie, before Week 24), the participant will have an early WD visit and will enter the 48-week follow-up period, unless the participant withdraws consent from study participation.

If a participant prematurely discontinues PegIFN- α 2a (ie, before Week 23 [Arms 1 and 2] or before Week 11 [Arm 3]), treatment with JNJ-3989 and NA should be continued as planned.

If the reason for withdrawal from the study is withdrawal of consent, then the participant will be offered an optional safety follow-up visit (to occur on the day of consent withdrawal). Study intervention assigned to the participant who discontinued study intervention may not be assigned to another participant.

7.1. Discontinuation of Study Intervention

Treatment with JNJ-3989 (and PegIFN- α 2a if applicable) must be discontinued prematurely if any of the discontinuation criteria listed below are met. Criteria specific for this ISA are highlighted (colored fill). For the few criteria from the Master Protocol that are specified or more restricted in this ISA, the changes compared to the Master Protocol are also highlighted (colored fill). If JNJ-3989 is prematurely discontinued, PegIFN- α 2a (if applicable) should also be discontinued. If PegIFN- α 2a is prematurely discontinued (ie, before Week 23 [Arms 1 and 2] or before Week 11 [Arm 3]), treatment with JNJ-3989 and NA should be continued as planned. NA treatment may be continued or, in consultation with the Sponsor, discontinued based on investigator judgement.

The discontinuation criteria are:

- The participant withdraws consent to receive study intervention.
- The investigator believes that for safety or tolerability reasons (eg, AE) it is in the best interest of the participant to discontinue JNJ-3989 (and PegIFN- α 2a, if applicable).
- The participant becomes pregnant.
- The participant has a \geq Grade 3 rash (see Section 10.6, Appendix 6: Rash Management) or allergic reaction (see Section 8.3.7.3, Acute Systemic Allergic Reactions).
- The participant has signs of hepatic decompensation (ie, clinical evidence of ascites, bleeding varices, or hepatic encephalopathy) or an increase in direct bilirubin $>1.5\times$ ULN in combination with INR $\geq 1.5\times$ ULN or albumin <3.0 g/dL. Treatment with JNJ-3989 should be discontinued and alternative treatment options (outside the study) should be considered in discussion with the Sponsor.
- The participant has a confirmed \geq Grade 3 eGFR abnormality and a drop from baseline of >10 mL/min/ 1.73 m², considered at least possibly related to JNJ-3989 (or PegIFN- α 2a, if applicable) that persists despite changing tenofovir disoproxil to ETV or TAF (if the patient was receiving tenofovir disoproxil) (see Section 8.3.7.2, Renal Complications).
- The participant has a QTcF prolongation (defined as a QTcF value of >500 ms, or an increase from baseline of >60 ms) at any given time point.
- The participant requires ≥ 7 days of treatment with any of the disallowed medications listed in Section 6.8, Concomitant Therapy, and does not intend to discontinue treatment with the disallowed medication.
- The participant has confirmed HBV virologic breakthrough (ie, confirmed on-treatment HBV DNA increase by >1 log₁₀ IU/mL from nadir or confirmed on-treatment HBV DNA level >200 IU/mL in participants who had HBV DNA level $<$ LLOQ of the HBV DNA assay).

If virologic breakthrough occurs during PegIFN- α 2a administration, this does not automatically lead to stop of JNJ-3989 and/or PegIFN- α 2a, but should be assessed/discussed with the Sponsor.

In case of virologic breakthrough, a viral sequencing sample will be collected during an unscheduled visit within 7 days of the DNA increase.

- The participant has ALT/AST elevations, as described in Section 8.3.6.2, Intervention-emergent ALT/AST Elevations.

Note: The grades are based on the DAIDS Toxicity Grading Scale (see Section 10.9, Appendix 9: DAIDS Table).

In addition, PegIFN- α 2a must immediately be discontinued for any of the following reasons:

- Participant has platelet count $<25,000$ cells/mm³.
- Participant has ANC <500 cells/mm³.

Note: PegIFN- α 2a treatment can be restarted when ANC values return to more than 1,000 cells/mm³ (see details in Section 6.5, Dose Modification)

- Participant develops evidence of hepatic decompensation during treatment, or ALT increase clinically significant or accompanied by direct bilirubin increase.
- Participant develops thyroid disorders or diabetes during treatment and cannot be controlled with medication.
- Participant develops new or worsening ophthalmologic disorders.
- Participant develops any deterioration of cardiovascular status.
- Participant develops serious, acute hypersensitivity reaction (eg, urticaria, angioedema, bronchoconstriction, anaphylaxis).
- Participant develops serious infection (bacterial, viral, fungal) and sepsis.
- Participant develops persistent or unexplained pulmonary infiltrates or pulmonary function impairment.
- Participant with onset or worsening of psoriatic lesion.
- Participant develops moderate or severe depression, or other psychiatric symptoms (for mild depression, treatment discontinuation may be considered).

Note: Participants who develop a neuropsychiatric AE during PegIFN- α 2a treatment, will be monitored closely until the neuropsychiatric AE resolves, with frequent (at least weekly) follow-up phone calls.

- Participant develops colitis symptoms (such as but not limited to abdominal pain, bloody diarrhea, and fever).
- Participant develops symptoms or signs suggestive of pancreatitis.

For participants who prematurely discontinue PegIFN- α 2a, treatment with PegIFN- α 2a may be restarted according to the recommendations from the locally approved prescribing information for PegIFN- α 2a.

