All participants will receive the last dose of JNJ-3989 at Week 24 and the last dose of PegIFN- α 2a at Week 23 (Arms 1 and 2) or Week 11 (Arm 3). They will start the FU Period after the Week 24 visit. If the protocol-defined NA treatment completion criteria (described in Section 6.5.1, NA Treatment Completion) are met based on the Week 24 results, treatment with NA will be stopped at the next scheduled visit (ie, FU Week 2), otherwise NA treatment will continue during the complete FU Period. **Note:** Participants who are close to meeting the protocol-defined NA treatment completion criteria with the Week 24 results, and do meet the criteria based on the FU Week 2 results may be allowed to stop NA at FU Week 4, after consultation with the Sponsor.

The NA treatment completion criteria which take ALT, HBV DNA, HBeAg, and HBsAg levels into consideration, have been selected to ensure that only participants with a higher chance of achieving sustained off-treatment response are allowed to stop all study intervention. Across a range of studies, HBsAg levels at end of treatment below 100 IU/mL were consistently associated with favorable off-treatment response (Jeng 2018; Papatheodoridis 2018).

Participants will be monitored closely during the 48-week FU Period and participants who completed NA treatment should re-start NA treatment if NA re-treatment criteria are met (see Section 6.5.2, NA Re-treatment Criteria During Follow-up, for more details).

Follow-up Procedures and Criteria for Re-initiation of NA Treatment

To ensure safety of patients during the FU Period, an ALT flare management plan is in place, including weekly visits for patients with ALT/AST $\geq 3x$ ULN and $\geq 3x$ nadir (ie, lowest value during study participation) until stabilization.

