During the study, participants will continue the same NA treatment (ETV, tenofovir disoproxil, or TAF) they were receiving at the time of screening (and during at least 3 months prior to screening). In case participants experienced toxicity to ETV, tenofovir disoproxil, or TAF prior to screening, they should be treated with one of the other two NAs during this study. If clinically indicated, switching from one NA treatment (ETV, tenofovir disoproxil, or TAF) to another NA treatment (ETV, tenofovir disoproxil, or TAF) during the study is allowed after consultation with the Sponsor.

For PegIFN- α 2a, the first administration must be performed at the study site by the investigator or his/her designee. Thereafter, weekly administration should preferably be done on the same day of the week in the evening by self-injection.^a Study site personnel will instruct participants on how to self-administer, where applicable, their PegIFN- α 2a injections at home. Used PegIFN- α 2a syringes should be separated from the needle via the sharps container and then placed into their original box and returned to the site at the next study visit, if allowed per local guidelines and regulations. The used needles in the sharps container will be returned to the study site after completion of the Treatment Period or disposed of following local standard procedures. If desired, participants can also choose to have the weekly administration of PegIFN- α 2a performed at the study site irrespective of the time of day.

JNJ-3989 and PegIFN- α 2a should be injected subcutaneously and the approximate location should be recorded. If both are injected in the abdomen, different areas of the abdomen should be used.

For a definition of study intervention overdose, refer to Section 6.7, Treatment of Overdose.

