8.3.7.3. Acute Systemic Allergic Reactions

Grade 1 (Localized Urticaria [Wheals] With no Medical Intervention Indicated)

Participants may continue the intake of study interventions.

Cetirizine, levocetirizine, topical corticosteroids or antipruritic agents may be prescribed.

Participants should be advised to contact the investigator immediately if there is any worsening of the acute systemic allergic reaction.

Grade 2 (Localized Urticaria With Intervention Indicated, or Mild Angioedema With no Intervention Indicated)

Participants may continue the intake of study interventions.

Cetirizine, levocetirizine, topical corticosteroids or antipruritic agents may be prescribed.

Participants should be advised to contact the investigator immediately if there is any worsening of the acute systemic allergic reaction, in which case the participant will permanently discontinue the intake of JNJ-3989 (and PegIFN- α 2a if applicable). Rechallenge is not allowed. The participant's NA treatment may be discontinued based on investigator judgement in consultation with the Sponsor.

Grade 3 (Generalized Urticaria, Angioedema With Intervention Indicated, or Symptoms of Mild Bronchospasm) and Grade 4 (Acute Anaphylaxis, Life-threatening Bronchospasm, or Laryngeal Edema)

Participants will permanently discontinue the intake of JNJ-3989 (and PegIFN- α 2a if applicable). Rechallenge is not allowed. The participant's NA treatment may be discontinued based on investigator judgement in consultation with the Sponsor.

Participants will be treated as clinically appropriate. Participants should be followed until resolution of the AE and standard management should be undertaken.

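### After early JNJ-3989 discontinuation, Protocol 7.1 and 6.5.1 give different grounds for stopping NA, and SAP Table 13 items 45 and 46 do not follow the NA completion criteria

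*Protocol*

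**What the plan says.** **Stopping NA after early JNJ-3989 discontinuation.** Protocol 7.1: "NA treatment may be continued or, in consultation with the Sponsor, discontinued based on investigator judgement". Protocol 6.5.1, for the same event: "NA treatment may be continued or, in consultation with the sponsor, discontinued, based on the above-mentioned NA treatment completion criteria". The criteria are ALT <3x ULN, the HBV DNA rule (<60 IU/mL at Week 24 with the previous value below LLOQ, or below LLOQ at Week 24), HBeAg-negative status, and HBsAg <100 IU/mL. Protocol 8.3.6.2 and 8.3.6.3 keep the participant on NA when JNJ-3989 is stopped for ALT/AST elevation or for hematologic abnormalities. For serious allergic reactions, 8.3.7.3 states "NA treatment may be discontinued based on investigator judgement in consultation with the Sponsor", and Appendix 6 Table 4 does the same for Grade 3 and 4 rash.

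**SAP deviations.** SAP 5.4.1.1.1 repeats the four criteria. Table 13 item 45 describes a participant who stopped NA at Week 24 despite relevant changes in ALT, HBV DNA or HBeAg at Week 20, or another preventing event. Item 46 describes one who did not stop at Week 24 although no such change or event was seen. Neither mentions HBsAg. Both are flagged as intercurrent events, and both lead to per-protocol exclusion if classed as major on case-by-case review.

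**Monitoring.** Under Protocol 8.3.6.2, management starts at ALT and/or AST at least 3x ULN and at least 3x nadir. Weekly monitoring ends when both enzymes are below 5x ULN and HBV DNA is below 20,000 IU/mL; Schedule of Activities footnote d repeats this end rule. Section 4.2 instead describes weekly visits from the same trigger until stabilization.

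**The concern.** Amendment 1 added the completion criteria after a severe flare off NA in another study. Section 4.2 gives their purpose as ensuring that "only participants with a higher chance of achieving sustained off-treatment response are allowed to stop all study intervention". Section 7.1 opens a second route off NA that does not mention them. An investigator and the Sponsor's medical contact could apply different standards to the same patient, each with text to cite.

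The SAP rows raise a different problem. A deviation definition that describes correct conduct fills the deviation tables with false entries. It also leaves per-protocol membership to a reviewer overriding the written rule.

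The monitoring wording matters most where liver function is impaired. In that branch of 8.3.6.2 the end condition asks for symptom improvement, if symptoms were present, but not for recovery of INR, direct bilirubin or albumin.

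**Working it through.** There is no plan figure to reproduce. The check compares the rules with each other.

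**1. Section 7.1 against 6.5.1.** The sentence just before the NA sentence in 7.1 says that JNJ-3989 and NA continue when only PegIFN-α2a is stopped. The NA sentence therefore concerns JNJ-3989 discontinuation, the event that 6.5.1 also covers. Cases:

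- *HBsAg ≥100 IU/mL, other three criteria met:* 6.5.1 does not allow NA to stop; 7.1 does.
- *"The participant has confirmed HBV virologic breakthrough", through the limb of HBV DNA >200 IU/mL:* 200 exceeds 60, so while that level persists the HBV DNA criterion fails. 6.5.1 does not allow NA to stop; 7.1 does.
- *"The participant has signs of hepatic decompensation":* if the ALT/AST trigger is also met, 8.3.6.2 keeps NA going. If not, 7.1 says only that JNJ-3989 stops and that treatment outside the study is discussed with the Sponsor.
- *"The participant withdraws consent to receive study intervention":* the criteria cannot bind someone who declines the drug, so a named exception is needed.

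**2. Items 45 and 46 against the criteria.** Four met/not-met criteria give 2^4 = 16 combinations. Assume that a relevant change means failing the same cut-off. The table's three markers then disagree with the four criteria in 1 of 16: ALT, HBV DNA and HBeAg acceptable, HBsAg ≥100 IU/mL. There the protocol requires NA to continue, and item 46 counts continuing as a deviation.

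Timing adds a second mismatch. Under 6.5.1, NA stops at FU Week 2, or at FU Week 4 for near-misses. FU Week 2 has target follow-up Day 15, so 15 − 1 = 14 days after the Week 24 visit. With the three markers unchanged and no other event noted, both compliant paths fit item 46:

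- HBsAg <100 IU/mL: the participant stops at FU Week 2, and so did not stop at Week 24.
- HBsAg ≥100 IU/mL: the participant stays on NA, and so did not stop at Week 24.

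In reverse, a participant who stops at FU Week 2 without meeting the criteria is not described by item 45, which covers only stops at Week 24.

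*Effect on analyses.* SAP 5.3.2 turns an intercurrent-event deviation into non-response only if Week 24 data are missing. SAP 5.3.2.1.4 already makes missing Week 24 data non-response. The FAS primary result is the same with or without the flag. What can change is per-protocol membership, deviation reporting and, for a flagged participant with missing Week 24 HBsAg, sensitivity estimators 2 and 3 (non-responder instead of dropped or filled from a nearby visit).

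**3. Monitoring trigger against end condition.** In ULN units, the trigger is ALT ≥ max(3, 3 × nadir) and the end condition is ALT <5.

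| Nadir (x ULN) | Trigger (x ULN) | ALT values meeting both (x ULN) |
|---|---|---|
| ≤1.0 | 3.0 | 3.0 to <5 |
| 1.3 | 3.9 | 3.9 to <5 |
| 1.6 | 4.8 | 4.8 to <5 |
| 1.9 | 5.7 | none |

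The overlap vanishes once 3 × nadir ≥ 5, that is at nadir ≥ 5/3 ≈ 1.67x ULN. AST and HBV DNA must also satisfy the end condition. The HBV DNA part is plausible on NA, since entry requires <60 IU/mL.

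If weekly visits lapsed, the schedule would govern. The longest gap is 28 days on treatment, and 57 − 29 = 28 days off NA after FU Week 4. Gaps of 85 − 29 = 56 and 169 − 85 = 84 days arise only for participants on NA whose HBV DNA and ALT are stable (footnote d).

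**The case against.** **On NA stopping.** Section 7.1 is general and 6.5.1 specific, so the specific rule could be taken to govern. The investigator also assesses the completion criteria (8.1), so judgement might mean judgement about them. But 7.1 does not refer to the criteria, and its wording resembles 8.3.7.3 and Table 4, where judgement is a separate basis for safety-driven stops. That may be what 7.1 intended, but it does not say so. Two parts of the defence stand. Sponsor consultation applies under both texts, so a reader who infers a unilateral stop goes too far. Nor are such participants left unmonitored: although 6.5.2 names only those who met the criteria, footnotes d and ww apply the 4-weekly visits, re-test triggers and immediate re-start to anyone off NA.

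**On the SAP rows.** The other-events clause in item 46 could absorb HBsAg ≥100 IU/mL, exclusion needs classification as major, and NA conduct after Week 24 cannot alter Week 24 HBsAg. These points limit the harm; they do not make the definition correct.

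**On monitoring.** This defence is the strongest. The end rule speaks of enzymes returning below 5x ULN, which implies a higher earlier value. A confirmatory visit within 7 days of receiving the result applies in any case. The impaired-function branch stops JNJ-3989, keeps NA and also refers to good clinical practice. Section 2.3.3 requires clinically significant abnormalities persisting at early discontinuation to be followed to resolution or agreed stabilization. The Appendix 7 flowchart is not in the text available and may settle the matter. A reader might infer that an active flare could wait 56 or 84 days for a visit. The documents do not support that, because those gaps require stable ALT and HBV DNA. A reader might also conclude that the end threshold should be 3x ULN. That is a clinical preference, and it would break the match with 6.5.2 and footnote ww, which both use 5x ULN.

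**Conclusion.** Two points are wrong as written: the basis for stopping NA in 7.1 conflicts with 6.5.1, and SAP items 45 and 46 do not match SAP 5.4.1.1.1 or the FU Week 2/4 stop. The third, the end condition for weekly monitoring, is minor. It disagrees with 4.2 only on a literal reading, and its clearest gap is the absence of any INR, direct bilirubin or albumin condition in the impaired-function branch.

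The number of participants affected cannot be estimated from the documents. Power, alpha and the FAS primary analysis do not change, so no reader should infer that the primary result is at risk. The per-protocol consequence depends on case-by-case classification, and the 1-in-16 count on reading a relevant change as failing the protocol cut-off. The monitoring point depends on Appendix 7 not already resolving it.

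**What to change.** 1. **Protocol 7.1:** state that after early JNJ-3989 discontinuation NA may be stopped only if the 6.5.1 criteria are met. List the exceptions, each in consultation with the Sponsor: withdrawal of consent to study intervention; pregnancy; rash or allergic reaction as already provided in Table 4 and 8.3.7.3; and NA toxicity not resolved by switching NA, which 6.1 says "during the study is allowed after consultation with the Sponsor" when clinically indicated. Keep the rules in 8.3.6.2 and 8.3.6.3 that NA continues.

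2. **SAP Table 13, items 45 and 46:** restate both with the four criteria of SAP 5.4.1.1.1, including HBsAg <100 IU/mL, and with FU Week 2 or FU Week 4 as the stopping visit. Do this before database lock, when the list is to be finalized anyway.

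3. **Protocol 8.3.6.2 and footnote d:** keep the 5x ULN limit. Add that weekly monitoring continues until ALT and AST have stabilized, as in 4.2, and until any abnormal INR, direct bilirubin or albumin has recovered or stabilized. Check that Appendix 7 agrees.

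The cost is a protocol wording change and two edited SAP rows. The only burden on participants is a few extra weekly visits and blood draws, mainly for elevations between 3x and 5x ULN.
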